## **2. Objectives (include all primary and secondary objectives)**

Specific Aim 1: To test whether nasal CPAP reduces the incidence of hypoxia during procedural sedation with propofol as compared to usual care. Hypothesis: A randomized clinical trial of an intervention to reduce airway obstruction (nasal CPAP) will decrease the incidence of hypoxic events ( $<90\% \geq 15s$ ) compared to usual care in patients undergoing procedural sedation.

Specific Aim 2: To determine the duration, magnitude and mechanism of hypoventilation and its association with hypoxia in subjects undergoing procedural sedation. Hypothesis: By determining minute ventilation, transcutaneous CO2 and sedation depth while measuring end-tidal CO2, it will be possible to relate ventilation to hypoxic events, sedation depth and airway obstruction. Further, reductions in the incidence of hypoxia in the intervention group will be consistent with the hypothesis that loss of airway motor tone underlies hypoventilation and associated hypoxia.

Specific Aim 3: To characterize the physiologic state when end-tidal capnography is insufficient for detecting hypoventilation. Hypothesis: The amplitude of the capnographic signal is not representative of the adequacy of ventilation due to artifact from loss of airway motor tone during procedural sedation.

Specific Aim 4: To determine if there short chain fatty acid serum concentration is protective for procedural sedation induced hypoventilation, obstruction and hypoxia: Hypothesis: Higher concentration

of short chain fatty acids will be reduce the risk of hypoventilation, obstruction, and hypoxia and suggests a link between respiratory function and gut microbiome.

**3. Background** (briefly describe pre-clinical and clinical data, current experience with procedures, drug or device, and any other relevant information to justify the research)

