Impedance based respiratory volume monitoring has been used to assess adequacy of ventilation and airway obstruction in patients undergoing endoscopic gastrointestinal procedures. In fact, such studies also suggest that EtCO2 often decreases as minute ventilation decreases. In this study, changes in minute ventilation from baseline, and episodes of upper airway obstruction will be assessed using the commercially available ExSpiron™ (Exspiron, Respiratory Motion Inc, Waltham MA). Previous studies using the ExSpiron™ have suggested that decreased minute ventilation during sedation for GE procedures is primarily due to decreased tidal volume rather than respiratory rate. Transcutaneous carbon dioxide has proven to closely approximate to arterial carbon dioxide (PaCO2), and in fact more closely reflects PaCO2 than end tidal carbon dioxide (EtCO2). Transcutaneous carbon dioxide (TcCO2) has been shown to closely correlate with PaCO2. After approximately 5 minutes of calibration time, it appears to track changes in PaCO2 with a lag time of 30 seconds to 2 minutes. In our experience using the TcCO2 monitor

for clinical application during jet ventilation, we have found the device to consistently track within 5 points of the PaCO2. (Sentec, Therwil, Switzerland).

Depth of anesthesia using processed electroencephalography has been described as a marker for depth of anesthesia during GETA and MAC with sedation. Depth of anesthesia using bispectral index (BIS) has been relatively well established and is known to correlate well with other measures of depth of anesthesia. We will use bispectral index (BIS) (Medtronic, Minneapolis, Minnesota) as a marker of state. In addition, all clinical data utilized in routine practice will be recorded, including drug dosing, method of drug administration, and length of stay in the recovery area.

Recently, alterations in the gut microbiome have been implicated in obesity, hypertension, obstructive sleep apnea induced hypertension, and airway smooth muscle tone that may relate to reactive airway disease. In general, lower short chain fatty acid levels are associated with pathology, and higher levels appear to be

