This study is a randomized controlled trial comparing oxygen delivery by nasal mask with CPAP versus standard care (nasal cannula or standard facemask) during propofol-based sedation for GE procedures to reduce the incidence of hypoxia. The primary outcome will be the rate of oxygen desaturation below 90% for  $\geq 15$  seconds. In addition, secondary measures will include evaluation of mechanism and degree of respiratory depression associated with hypoxia and hypoventilation by characterizing changes in minute ventilation, tidal volume, and respiratory rate as well as the rate and degree of airway obstruction. We hypothesize that the addition of Nasal CPAP in the intervention arm will lead to decreased obstruction as positive pressure will stent open the obstructed airway. Depth of anesthesia will be monitored by BIS and we hypothesize that the degree of hypoventilation, obstruction, and will be significantly lower in the intervention arm compared to the control arm. Further, the depth of anesthesia will be independent of total propofol dose received. While the primary outcome in this study is hypoxia, we also seek to marry ETCO2 with minute ventilation and transcutaneous CO2 to better understand the total effects of sedation on respiration. Thus, the study will also serve to evaluate which mode(s) of respiratory monitoring might be the best possible intervention to enhance safety during procedural sedation. Further, we suspect that the amplitude of ETCO2 will not predict the degree of respiratory depression seen with other monitors. In addition, we will measure serum short chain fatty acid concentrations as a predictor and possible mechanism for differences in individual variability in anesthesia induced respiratory depression.

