All subjects enrolled in the study will have research monitors placed on the skin in a similar fashion to the pads for ekg lead placement, with respiratory volume monitoring on the chest, BIS and TcCO2 on the forehead. All enrolled subjects will be connected to the ExSpirom™ monitor (Respiratory Motion, Inc., Waltham MA) and digital respiratory traces of MV, TV, and RR measurements will be collected on all 240 patients. The ExSpirom monitor uses an adhesive, latexfree, adjustable 5 sensor strip applied to the chest to measure the amount of air moving in and out of the lung in real time. Minute ventilation will also be correlated to transcutaneous CO2 as measured by the SenTec Digital Monitor (SenTec AG, Therwil, Switzerland). Transcutaneous CO2 (Ptc CO2) monitoring provides a noninvasive technique allowing continuous monitoring of ventilation. It is based on arterialization of the capillary bed through the local application of heat and the use of Stow-Severinghaus electrodes. The sensor will be calibrated, applied to the patient's forehead, cheek, or chest, and warmed to a constant surface temperature of 42 °C. In adults, these temperatures are safe for up to 24h, and the procedures performed in this study are generally less than 2 hours. The BIS monitor is also an adhesive strip with 4 sensors applied to the subjects forehead.

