## 7. Study Statistics

### a. Primary outcome variable.

The primary outcome will be the rate of hypoxia below 90% for  $\geq 15$  seconds.

- ### b. Secondary outcome variables. Secondary outcomes will include change in respiratory parameters (tidal volume, respiratory rate, minute ventilation, obstructive events), hypoventilation by TcCO2, EtCO2, and depth of anesthesia by BIS, as well as demographic differences. Demographic information to the occurrence of hypoxic events will be analyzed with logistic regression.

Statistical plan including sample size justification and interim data analysis.

Power analysis is based on a previous German study in the literature, of patients undergoing upper and lower endoscopy with hypoxia rates of 13.5% with standard care and 1.8% with application of nasopharyngeal airway. Using these figures to perform a power analysis for the primary outcome of hypoxia below 90%, with alpha 0.05 and power of 0.9, approximately 109 subjects in each arm or a total of 218 subjects will be needed. In order to obtain 109 completed subjects in each arm and to allow for those participants with incomplete datasets (e.g. monitor failure), we will enroll 120 subjects in each arm and a total of 240 subjects.

Frequency data will be analyzed with Fisher's Exact Test, ordered categorical data will be analyzed with the rank sum test, and continuous data will be analyzed with regression or equivalent techniques. Therefore, our primary outcome as to the incidence of hypoxia in each arm of the study will be determined using Fisher's exact test. All time series data from multiple sources will be aligned using the associated time stamp with the aid of the program data manipulation capabilities in Mathematica 11. Longitudinal analysis will be performed using a mixed model approach, initially with random intercepts alone, with the addition of nonlinear terms and interaction as indicated by the resulting model. Throughout, findings will be considered significant for  $p < 0.05$  and  $p$  values will be determined using two-sided tests. Statistical analysis will be performed with the aid of Stata 13. An analysis will be performed after the first 20 subjects to ensure complete data collection and to run a batched analysis of SCFA to evaluate this aim. An interim data analysis will be done after ~120 subjects have been enrolled.

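### The longitudinal mixed model names no step for serial correlation in the monitor traces, so tests relating one trace to another within patients are likely to be too liberal

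*Combined protocol and SAP*

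**What the plan says.** Section 7 (Study Statistics) says of the monitor data: "All time series data from multiple sources will be aligned using the associated time stamp". The next sentence prescribes a mixed model for longitudinal analysis, "initially with random intercepts alone, with the addition of nonlinear terms and interaction as indicated by the resulting model". The same paragraph sets one significance rule: "Throughout, findings will be considered significant for" p below 0.05, two-sided.

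Section 4 (Study Procedures) describes the data: "digital respiratory traces of MV, TV, and RR measurements will be collected on all 240 patients". It adds: "Minute ventilation will also be correlated to transcutaneous" CO2.

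Aim 2 in section 2 (Objectives) states that "it will be possible to relate ventilation to hypoxic events, sedation depth and airway obstruction". Section 3 (Background) says the study will also serve to "evaluate which mode(s) of respiratory monitoring might be the best possible intervention to enhance safety during procedural sedation". It also reports that TcCO2 tracks arterial CO2 "with a lag time of 30 seconds to 2 minutes".

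No section mentions a residual correlation structure, robust or clustered standard errors, a bootstrap, or thinning or averaging of the traces into epochs. The primary outcome is assigned separately to Fisher's exact test.

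**The concern.** A random-intercept model treats a patient's records, given the intercept, as independent. Two readings a minute apart are taken to be as weakly related as two readings an hour apart. Continuous physiological signals rarely behave like that, and the lag reported for TcCO2 suggests persistence over short intervals. Nonlinear terms and interactions reshape the mean curve; they leave the within-patient error structure as it was.

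When outcome and covariate are both positively autocorrelated, the model counts more independent information than there is. A null association then passes p < 0.05 too often, and a real one gets too narrow an interval. The analyses exposed are those that relate ventilation, TcCO2 and sedation depth to each other. These carry Aim 2 and bear on the question of which monitor best serves safety.

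**Working it through.** **The plan's own figure.** Section 7 gives no figure for the longitudinal model. Its only planning figure is 109 per arm, from hypoxia rates of 13.5% and 1.8%, alpha 0.05 and power 0.9. The two-sided pooled formula without continuity correction gives 107, and exact Fisher power at 109 per arm is 0.908. The figure is sound and does not depend on the point made here. It supplies the number of patients used below: 2 × 109 = 218.

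**Inputs that must be assumed.** The document gives neither the epoch nor the autocorrelation. I took lag-1 autocorrelations of 0.3, 0.6 and 0.9, and 20, 60 or 80 records per patient, or 11 to 120. The last range is one record per minute for procedures of more than 10 minutes (section 5) and generally less than 2 hours (section 4).

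**Closed form.** Let re and rx be the lag-1 autocorrelations of residual and covariate, both first-order. For long traces, the true variance of the within-patient slope divided by the random-intercept model's variance is

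q = (1 + re·rx) / (1 − re·rx),

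and the actual error of a nominal 5% two-sided test is 2[1 − Φ(1.96/√q)].

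| re = rx | re·rx | q | √q | actual error |
|---|---|---|---|---|
| 0.3 | 0.09 | 1.09/0.91 = 1.20 | 1.09 | 7.3% |
| 0.6 | 0.36 | 1.36/0.64 = 2.13 | 1.46 | 17.9% |
| 0.9 | 0.81 | 1.81/0.19 = 9.53 | 3.09 | 52.5% |

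**Simulation.** 218 patients, patient intercept SD 1, AR(1) residual SD 1, AR(1) covariate SD 1 with between-patient SD 0.7, and 1,000 trials per setting (Monte Carlo standard error 0.7 points at 5%, 1.6 at 50%). Error for a null covariate with model-based standard errors:

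| records per patient | 0.3 | 0.6 | 0.9 |
|---|---|---|---|
| 20 | 7.4% | 15.3% | 37.6% |
| 60 | 7.3% | 16.0% | 46.2% |
| 80 | 7.8% | 17.9% | 48.9% |
| 11-120 | 8.1% | 19.0% | 52.2% |

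Separately written simulations gave 14% at 0.5 (60 records), 23% at 0.7 (20 records), 32% at 0.8 (60 records) and 47-50% at 0.9 (60 and 180 records). With a true slope of −0.3 (20 and 11-120 records), nominal 95% intervals covered 93-94%, 83-84% and 50-65% at 0.3, 0.6 and 0.9.

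**TcCO2 case.** Read the 30-second to 2-minute lag as a first-order time constant with one-minute records. Residual lag-1 is then exp(−1/0.5) = 0.135 to exp(−1/2) = 0.607. For covariate lag-1 of 0.3, 0.6 and 0.9:

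- 30 seconds: simulated error 6.1%, 7.6%, 7.8% (closed form 6.0%, 7.1%, 8.3%).
- 2 minutes: simulated error 10.8%, 18.0%, 26.9% (closed form 10.3%, 18.1%, 28.8%).

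**Where there is no problem.** With no autocorrelation, error is 3.9-6.5%. With a white-noise covariate in the TcCO2 case it is 4.4-5.6%. For the between-arm mean difference it is 3.6-6.3%.

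**Do nonlinear terms in time help?** Adding quadratic and cubic time terms left the covariate error essentially unchanged, at 7-8%, 16-18% and 38-47% for 0.3, 0.6 and 0.9 (20 or 60 records).

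**If the unspecified interaction were arm by time.** Error would be 14-15%, 29-33% and 50-63% with random intercepts only. A random slope restores it to 4.3-5.0%, but leaves the null-covariate error at 5.0%, 13.7% and 26.0% (20 records, 300 trials each).

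**Clustered standard errors.** Clustering on patient gave about 4-7% error in the same settings, and 94-96% coverage.

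**The case against.** The strongest reply is that the harm depends on an analysis the plan never spells out. No section says the trace-to-trace relations will be fitted with this model. Section 4 speaks only of correlating, and section 7 also allows regression or equivalent techniques for continuous data. The secondary outcomes might simply be compared by arm, where there is no problem. This stands, and the conclusion is conditional for that reason. But the mixed model is the only method named for longitudinal data and directly follows the alignment step. The regression alternative as stated has no step for serial correlation either.

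Second, the wording describes a starting model to be extended. That is fair, but the additions named are mean-model terms, no diagnostic for serial correlation is mentioned, and polynomial time terms did not help in simulation. That simulation used stationary AR(1) noise; a slow trend common to patients could be partly absorbed.

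Third, the size is assumed. This stands. A pure delay in TcCO2 would not imply autocorrelation at all, and at the 30-second reading the inflation is minor. Both traces must be autocorrelated for the effect to appear.

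Fourth, minute ventilation and TcCO2 are probably truly related, so false positives matter little for that pair. Agreed; there the damage is interval coverage. The arm-by-time figures rest on an interpretation that no section supports and should carry no weight in judging importance.

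**Conclusion.** The concern holds, within limits. The longitudinal model as written has no step for serial correlation. If it is used to relate one autocorrelated trace to another within patients, its model-based standard errors are likely to be too small. The true SD of the slope is 1.1 to 3.0 times the model's standard error over lag-1 autocorrelations of 0.3 to 0.9, so the effect runs from minor to large. Where in that range the trial lies cannot be settled from the document. The result rests on first-order positive autocorrelation in both series and on the assumed record counts. It concerns secondary, mechanistic results only.

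**What to change.** Add one sentence to the statistical plan in section 7: *Inference from all longitudinal mixed models will use standard errors clustered on patient.* With about 218 patients there are enough clusters. At the interim size of 120 patients (20 records each) clustered errors still gave 4.7-6.6%. A serially correlated residual structure may be added but is optional. A random slope alone is not a substitute, because it does not cure the covariate problem.

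The change needs no new data or patients and leaves the primary analysis alone. Its cost is wider intervals for the mechanistic associations, some of which may lose significance.

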### c. Early stopping rules.

Stopping will be considered if the intervention shows clear benefit at the midpoint of the study, or if it clearly shows no benefit.

## 8. Risks

- ### a. Medical risks, listing all procedures, their major and minor risks and expected frequency. All subjects will have, as a part of routine care, 5 ECG pads. The ExSpiron™ padset adds no more risk to the care of the subjects than does the 5 ECG pads routinely applied to the chest. The BIS padset is also very similar to the ECG pads, but will be placed on the forehead.

In the past, there was a risk of discomfort or skin burning in infants with the use of transcutaneous CO2 sensors. However, current monitoring technology differs from previous sensors in the use of lower temperatures (42 °C as opposed to 45–47 °C) which has been shown to dramatically decrease the risk for skin burning (Storre JH, Steurer B, et al. CHEST 132:1810–1816). In adults, the

recommendation by the manufacturer is to check the site every 24 hours; however, for purposes of this study, sensors will be in place for significantly shorter period of time

The SuperNova™ is a nasal anesthesia mask that can generate CPAP to maintain airway patency, provide ventilator support, and provide rescue nasal ventilation during procedural sedation and perioperative period. The most likely risk is a red mark on the face from the mask. Dry nose and mouth may occur, as can dry eyes, and a very unlikely risk of nose bleed. (In fact, a common rescue during standard therapy is to place a nasopharyngeal airway, which carries a higher risk of nose bleed). CPAP and ventilator interventions associated with the nasal mask carry similar risks to interventions that may be required in patients undergoing sedation who require additional ventilator support. b. Steps taken to minimize the risks.

Transcutaneous CO2 sensors will be maintained and operated on the same site for a maximum 8 hours after which the site will be assessed for any signs of irritation and the monitor will be moved or removed if indicated.

Careful placement of the Supernova mask will be performed and the fit adjusted as needed. c.

Plan for reporting unanticipated problems or study deviations.

If transcutaneous CO2 sensor sites demonstrate any signs of irritation, the sensor will be moved or monitoring discontinued as indicated.

Any unanticipated problem or study deviation will be reported to the IRB.

d. Legal risks such as the risks that would be associated with breach of confidentiality.

This study carries a low risk of loss of confidentiality. Multiple safeguards are in place to protect the confidentiality of the medical and demographic data. Each patient will be assigned a randomly generated number that will be linked to the medical record number. This file will be stored in a password protected spreadsheet and backed up to a network drive managed by the Department of Anesthesiology and Critical Care Medicine. Demographic and clinical data will be only linked to the random study number.

e. Financial risks to the participants. None

## 9. Benefits

a. Description of the probable benefits for the participant and for society.  
This study may provide no benefit to any particular patient.

The study may benefit society if a better method of delivering oxygen is demonstrated for a procedure that is performed in millions of patients every year. Further, the study may help us to better understand how patients breathe under anesthesia, which may help us to improve delivery of anesthesia care in the future.

## 10. Payment and Remuneration

a. Detail compensation for participants including possible total compensation, proposed bonus, and any proposed reductions or penalties for not completing the protocol. None

## 11. Costs

- a. Detail costs of study procedure(s) or drug (s) or substance(s) to participants and identify who will pay for them.

There will no costs for the monitors (the hospital has a separate supply) or the SuperNova masks used in the treatment arm of this study. Revolutionary Medical Devices will provide the SuperNova masks.

